7.2. Secondary Efficacy Endpoints and Analyses

7.2.1. Stool Consistency

Patients will be asked to record daily stool consistency according to the BSFS most representative stool consistency in the past 24 hours and the worst stool consistency (defined as the loosest stool with the highest BSFS score) in the past 24 hours. The patient-reported BSFS consistency score, based on a 1 to 7 scale where 1 corresponds to a hard stool and 7 corresponds to watery diarrhea (10), can be found in [Appendix 2](#).

The patient-reported stool consistency scores and change from baseline scores (averaged over the week prior to each visit) will be summarized descriptively by cohort for each scheduled timepoint. Pooled active treatment data will be compared to Placebo for the analyses, and by cohort, using a t-test of equal variances and a two-tailed alpha of 0.05 specified in section 7.1.1 for reference. Box plots of the BSFS scores (averaged over the week prior to each visit) will also be presented by cohort for each scheduled visit. Line plots of the BSFS change from baseline values (averaged over the week prior to each visit) will also be presented by cohort for each scheduled visit. Analyses for the most representative stool consistency in the past 24 hours and worst (loosest) stool consistency in the past 24 hours will both be presented.

Sponsor: Boston Pharmaceuticals, Inc.
Protocol Number: BOS-589-201
Version and Date: Version 1.2 12NOV2020

To evaluate the treatment effects in the subset of patients with fecal calprotectin under 50mcg/g at screening, this analysis of BSFS most representative consistency and BSFS worst consistency will be repeated as sensitivity analyses on this subgroup as described in section 7.1.1.

7.2.2. Stool Frequency

Patients will be asked to record stool frequency based on the total number of spontaneous bowel movements in the past 24 hours. Bowel movement frequency and change from baseline (averaged over the week prior to each visit) will be analyzed and summarized using the same method as the secondary endpoint described in Section 7.2.1.

To evaluate the treatment effects in the subset of patients with fecal calprotectin under 50mcg/g at screening, this analysis of stool frequency will be repeated as a sensitivity analysis on this subgroup as described in section 7.1.1.

7.2.3. Irritable Bowel Syndrome Severity Score

IBS-SS will be collected at only at the baseline, Day 29, and Day 43 visits. Patients will be asked to complete 5 questions regarding the severity of their IBS. Each of the 5 questions generate a maximum score of 100, leading to a total possible score of 500. IBS-SS will be analyzed and summarized using the same method as the secondary endpoint described in Section 7.2.1 (except only for scheduled visits of Baseline/Day 1, Day 29, and Day 43). Summaries performed by visit will include responses to the individual questions, as well as the total scores.

7.2.4. Irritable Bowel Syndrome Global Score

Patients will be asked to record daily their overall IBS-GS in the prior 24 hours. The patient-reported daily IBS-GS is based on a 0 to 4 scale where:

- 0 corresponds to no symptoms;
- 1 corresponds to mild symptoms;
- 2 corresponds to moderate symptoms;
- 3 corresponds to severe symptoms;
- 4 corresponds to very severe symptoms.

IBS-GS will be analyzed and summarized using the same method as the secondary endpoint described in Section 7.2.1.

Sponsor: Boston Pharmaceuticals, Inc.
Protocol Number: BOS-589-201
Version and Date: Version 1.2 12NOV2020

7.3. Exploratory Efficacy Endpoints and Analyses

7.3.1. Weekly Responder

Weekly responders will be summarized as an exploratory efficacy endpoint.

A patient is categorized as a weekly responder if the patient is a weekly responder in both pain intensity and stool consistency (page 8 of [FDA guidance document on IBS](#)).

- An Abdominal Pain Intensity Weekly Responder is defined as a patient who experiences a decrease in the weekly average of the WAP in the past 24 hours score of at least 30 percent compared with weekly average at baseline, i.e., $(\text{weekly average of baseline} - \text{weekly average of a post-baseline visit}) / \text{weekly average of baseline} \geq 0.3$
- A Stool Consistency Weekly Responder is defined as a patient who experiences a 50 percent or greater reduction in the number of days per week with at least one stool that has a consistency of Type 6 or 7 compared with weekly average at baseline, i.e., $(\text{weekly average of the number of Type 6 or 7 BSFS stool of baseline} - \text{weekly average of the number of Type 6 or 7 BSFS stool of a post-baseline visit}) / \text{weekly average of the number of Type 6 or 7 BSFS stool of baseline} \geq 0.5$

The number and percentage of patients who are abdominal pain intensity weekly responders, stool consistency weekly responder, and composite weekly responders in both will be summarized by cohort at each scheduled visit. A chi-square test will be used, as a reference, to test whether there is a difference by between each active dose level and Placebo, both active dose levels and Placebo, and between the two active dose levels. Fisher's exact test will be used if the expected values in any of the cells of the contingency table are below 5.

To evaluate the treatment effects in the subset of patients with fecal calprotectin under 50mcg/g at screening, this analysis of weekly responders will be repeated as a sensitivity analysis on this subgroup.

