5.1 Inclusion Criteria

In order to be eligible to participate in this study, an individual must meet all of the following criteria:

Age

1. Male and female patients must be 18 to 65 years of age, inclusive, at the time of signing informed consent.

Run-in eDiary Compliance

2. Patient has completed the daily electronic diary on at least 6 of the 7 days during the week prior to randomization AND at least 11 of the 14 days during the 2 weeks prior to randomization. Patients have up to 3 weeks to meet these criteria.

Type of Patient and Disease Characteristics

3. Patient meets the diagnosis of IBS based on the Rome IV diagnostic criteria (CCI [REDACTED]):*

- Recurrent abdominal pain occurring, on average, at least 1 day per week and associated with 2 or more of the following:
 - Related to defecation;
 - Associated with a change in frequency of bowel movements;
 - Associated with a change in form (appearance) of stool;

* These criteria must be fulfilled for the last 3 months prior to randomization and onset must have occurred at least 6 months prior to randomization.

4. Patient meets the diagnosis of IBS-D subtype based on Rome IV diagnostic criteria (CCI [REDACTED]). On days when the patient experiences IBS symptoms:

- At least 25% of stools are loose or watery; AND
- Fewer than 25% of stools are hard.

5. Over the final 7 days of the run-in period, the patient has an average of WAP scores in the prior 24 hours of 3.0 to 8.0 (on a 0 to 10 numerical rating scale, where 0 indicates no pain and 10 indicates worst pain imaginable).
6. Over the final 7 days of the run-in period, the patient has an average daily BSFS score ≥ 5.0 (on a 1 to 7 scale, where 1 = hard, lumpy stools, and 7 = watery, liquid stools), and there must be at least 2 days with stool consistency of Type ≥ 6 .
7. Patient is not planning to change his or her usual diet and lifestyle during the course of the study.

Diagnostic Assessments

8. Patient must undergo or previously have undergone (a) an appropriate evaluation for their IBS symptoms, including an evaluation for organic/structural etiologies (if in the presence of alarm symptoms); and (b) age-appropriate screening for colorectal cancer, if applicable.
 - a) If at least one of the following alarm features are present, then the patient must have had a colonoscopy that should include biopsy since the onset of symptoms or within the past 5 years (whichever is less):

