8.3.2 Bristol Stool Form Scale

Patients will be asked to record daily stool consistency according to the BSFS most representative of the past 24 hours and worst stool consistency (defined as the loosest stool with the highest BSFS score) in the past 24 hours. The patient-reported BSFS consistency score is based on a 1 to 7 scale where 1 corresponds to a hard stool and 7 corresponds to watery diarrhea (CCI [REDACTED]). Please refer to [Appendix 3](#).

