	average of the WAP in the past 24 hours score of at least 30% compared with baseline averaged over the week prior) and a stool consistency weekly responder (at least 50% reduction in the number of days per week with at least one stool that has a consistency of Type 6 or 7 compared with baseline averaged over the week prior), at each scheduled visit.

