7. EFFICACY

Efficacy analyses will be conducted using the ITT and PP Analysis Sets.

All available efficacy data will be provided in by-patient data listings on all ITT patients.

The efficacy objectives of the study are to evaluate the effect of BOS-589, relative to Placebo after 4 weeks of therapy, on pain, defecation, and key IBS-D related signs and symptoms.

During the 4 weeks of the double-blind treatment phase, patients will be required to access their electronic diary every day, preferably at the same time each day, to record IBS-D symptom data and information related to their bowel function and rescue medication use.

For all efficacy endpoints, the Day 29 visit change from baseline is the main timepoint of interest. However, unless stated otherwise, data will be presented for each planned visit (Baseline/Day 1, Day 8, Day 15, Day 22, Day 29, and Day 43).

For efficacy endpoints collected daily, the baseline score will be the average of non-missing scores reported for the last 7 days prior to the date where eligibility and run-in criteria pertaining to IBS-D symptom and bowel function have been met. The Day 29 visit score will be the average of non-missing scores reported during the 7 days prior to the Day 29 visit. The Day 8 visit, Day 15 visit, Day 22 visit, and Day 43 visit scores are calculated in a similar manner. If there are missing daily scores on any day, the visit score will be averaged from all the non-missing values during the 7 days prior to the visit. No imputation of the missing values will be made. For the Day 29 calculation only, a window of ± 14 days relative to actual calculated day 29 from dosing will be applied such that any Day 29 visit occurring outside that window will be excluded.

Sponsor: Boston Pharmaceuticals, Inc.
Protocol Number: BOS-589-201
Version and Date: Version 1.2 12NOV2020

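### The stool-consistency weekly responder is defined by days, but its formula counts stools and does not name the BSFS item

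*SAP*

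**What the plan says.** The verbal definition in SAP 7.3.1 requires at least a 50% "reduction in the number of days per week with at least one stool that has a consistency of Type 6 or 7". The endpoint table in SAP section 2 agrees: "stool consistency weekly responder (at least 50% reduction in the number of days per week with at least one stool". The unit in both is the day.

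The formula that follows in 7.3.1 is offered as a restatement, but its terms are the "weekly average of the number of Type 6 or 7 BSFS stool of baseline" and the matching post-baseline quantity. The unit there is the stool.

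On what the diary holds, Protocol v3.0 section 8.3.2 states: "Patients will be asked to record daily stool consistency according to the BSFS most representative of the past 24 hours and worst stool consistency". That is two BSFS scores per day. SAP 7.2.2 has patients "record stool frequency based on the total number of spontaneous bowel movements in the past 24 hours", a count that is not split by type. For the secondary stool endpoint, SAP 7.2.1 says that analyses of the "most representative stool consistency in the past 24 hours and worst (loosest) stool consistency in the past 24 hours will both be presented". SAP 7.3.1 names neither item.

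For diary endpoints with missing days, SAP section 7 says that "the visit score will be averaged from all the non-missing values during the 7 days prior to the visit", with no imputation.

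**The concern.** A definition and its formula should give the same answer. Here they use different units, and the formula, read literally, needs a quantity that was never collected. A programmer must therefore reinterpret it. The natural reinterpretation, counting days with a recorded score of 6 or 7, still leaves a choice between two BSFS items. Two people following 7.3.1 could produce different stool and composite responder tables from the same data, and a choice made after unblinding would be open to question. The quantities at stake are exploratory: the stool and composite responder rates at each visit, the chi-square or Fisher tests given for reference, and the repeat in patients with screening calprotectin under 50 mcg/g.

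**Working it through.** The documents state no responder rate or power, so there is no figure to reproduce. The check applies reduction = (baseline − visit)/baseline, with response if ≥ 0.5, to constructed patients.

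**1. Days and stools are not interchangeable.**
- Six days with 3 loose stools each, then six days with 1 each. Days: (6 − 6)/6 = 0%, non-responder. Stools: (18 − 6)/18 = 66.7%, responder.
- Four days with 1 loose stool each, then two days with 2 each. Days: (4 − 2)/4 = 50%, responder. Stools: (4 − 4)/4 = 0%, non-responder.

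These cases show only that the units differ. The stool count cannot be computed from this diary.

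**2. Which BSFS item matches the definition.** SAP 7.2.1 defines the worst item as the day's loosest stool, the one with the highest score. Worst ≥ 6 therefore holds exactly when at least one stool that day was Type 6 or 7. A representative score below 6 does not rule out such a stool.

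**3. The item changes the answer in both directions.** Each week has 7 recorded days, and the worst score is never below the representative score.

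| Patient | Item | Type 6/7 days, baseline then visit | Reduction | Responder |
|---|---|---|---|---|
| (a) | worst | 6 then 4 | 2/6 = 33% | no |
| (a) | representative | 4 then 2 | 2/4 = 50% | yes |
| (b) | worst | 4 then 2 | 2/4 = 50% | yes |
| (b) | representative | 2 then 2 | 0/2 = 0% | no |

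Both patients can meet inclusion criterion 6 of Protocol v3.0, which needs a mean of at least 5.0 and says "there must be at least 2 days with stool consistency of Type" 6 or above. In (a), representative scores of 6 on 4 days and 5 on 3 days average 39/7 = 5.57. In (b), 6 on 2 days and 5 on 5 days average 37/7 = 5.29.

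**4. Missing diary days.** Take 6 of 7 days at baseline, then 3 of 4 recorded days.
- Raw day count: (6 − 3)/6 = 50%, responder.
- Proportion of recorded days: (6/7 − 3/4)/(6/7) = 12.5%, non-responder.

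The raw count makes a responder out of unrecorded days. The proportion is the form consistent with the averaging in SAP section 7.

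**5. Zero baseline.** A patient who meets criterion 6 in the baseline week has at least 2 worst-item days at 6 or 7, whichever item was used for eligibility, because the worst score is at least the representative one. So p at baseline is at least 2/7 = 0.29.

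**The case against.** The strongest reply is that this is loose wording. Since stools by type are not recorded, the only thing that can be programmed is a count of daily records of 6 or 7, which is a count of days. The requirement for at least one such stool then points to the worst item. The mock shells are a separate document and may name it. This largely disposes of the difference in units as a numerical problem. It does not settle the item: 7.2.1 carries both, 7.3.1 leaves the choice to inference, and the formula on the page remains wrong.

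A second reply is that missing data are already covered. SAP section 4 bases percentages on non-missing values and shows missing values as a separate category, and section 7 averages the recorded days. That stands, and no new class of excluded patients is needed.

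A reader might go further and infer that patients with diaries under Protocol v2.0 create a gap, because that version collected only the representative item and its entry criterion set no minimum number of Type 6 days. The documents do not show that anyone was randomised under v2.0, so this should not be listed as a problem. Nor does missing stool status justify removing a patient from the composite. The composite requires both components, so a patient who fails on pain is a known non-responder; dropping such patients would inflate the composite rate.

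**Conclusion.** The point holds and is minor. The formula in SAP 7.3.1 contradicts the definition beside it and the SAP section 2 table, cannot be computed literally, and leaves the BSFS item unstated. The item can move a patient across the 50% threshold either way, as (a) and (b) show. How many patients would be reclassified cannot be calculated, because the documents give no distribution of diary scores.

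A reader might infer that the efficacy conclusions are at risk; they are not. The primary pain endpoint does not use BSFS, and the secondary stool analyses name both items and do not use this formula.

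The conclusion assumes that the diary holds only the items described in the protocol and SAP. If the mock shells specify the worst item, what remains is a correction to the SAP text.

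**What to change.** Replace the formula in SAP 7.3.1 with: p is the proportion of recorded diary days in the 7-day window on which the worst daily BSFS is 6 or 7; a patient is a stool-consistency responder if (p baseline − p visit)/p baseline ≥ 0.5.

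Add that a patient with no worst-item data, or with p = 0 at baseline, is shown as missing for the stool component under SAP section 4. For the composite, a patient who fails the pain criterion is a non-responder; only a pain responder with missing stool status is missing.

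The cost is a few sentences, using items already collected under Protocol v3.0. There is a small downside: with missing diary days, the proportion can classify a patient differently from a raw day count, as in step 4 (12.5% against 50%). The change sets no minimum number of recorded days, so a sparse week can still give an extreme p; that feature is shared with every weekly average in SAP section 7. The wording should be settled before unblinding.

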8. PHARMACOKINETICS / PHARMACODYNAMICS

PK/PD analyses are covered under a separate SAP.

9. SAFETY

Unless otherwise specified, all safety analysis reporting will be based on the SAF Analysis Dataset. For safety analyses, Day 29 represents measures taken at end of treatment/early termination while Day 43 represents measures taken at the end of study.

9.1. Adverse Events

AEs starting after the informed consent date until the Day 43/End of Study Follow-up visit will be recorded. AE assessments will include severity (mild, moderate, severe), relationship to study drug (related or not related), and seriousness. AEs with a missing severity will be classified as severe. AEs with a missing causality will be classified as related. AEs with missing seriousness will be classified as serious.

Any event reported on the CRF that occurs on or after the initiation of study drug is defined as a treatment-emergent adverse event (TEAE). Guidelines for categorizing an event as treatment-emergent based on start and stop dates and times are in Appendix 1. Additionally, an AE that is reported to have started on Day 1 without an associated onset time will be assumed to have occurred after the initiation of study drug. Hence, AEs occurring on Day 1 with no associated onset time will be assumed to be treatment emergent. SAEs associated with a protocol specified procedure and occurring after the time of consent but before administration of first dose of study drug will be defined as non-treatment emergent AEs (NTEAEs) and will be excluded from summary tables but will appear in listings flagged as NTEAE.

On a summary table, the number and percentage of patients in each of the following categories will be summarized by cohort following the cohort display in section 5.9:

- Any TEAE
- Any TEAEs related to study drug
- Any moderate or severe TEAEs
- Any moderate or severe TEAEs related to study drug
- Any treatment-emergent SAEs
- Any treatment-emergent SAEs related to study drug
- Any TEAEs causing discontinuation of study drug
- Any TEAEs with outcome of death
- Any TEAEs leading to withdrawal from the study

AEs will be coded to a SOC and PT using MedDRA (the version used will be defined in the study data management plan).

For summaries of TEAEs by SOC and PT, a patient will be counted once within an SOC, even if the patient experienced more than one TEAE within a specific SOC (likewise for PT). TEAEs will be ordered by descending frequency for overall SOC incidence followed by descending frequency of overall PT incidence. Summaries of TEAEs by SOC and PT will include the following:

- All TEAEs
- All TEAEs by severity
- All moderate or severe TEAEs
- All TEAEs related to study drug
- All treatment-emergent SAEs

Sponsor: Boston Pharmaceuticals, Inc.
Protocol Number: BOS-589-201
Version and Date: Version 1.2 12NOV2020

- All treatment-emergent SAEs related to study drug
- All TEAEs causing discontinuation of study drug
- All TEAEs with outcome of death
- All TEAEs leading to withdrawal from the study

All AEs, including the verbatim and coded terms, will be listed for all enrolled patients. Additional separate listings will be provided for all AEs with outcome of death, all AEs causing discontinuation of study drug, all SAEs, and all AEs leading to withdrawal from the study.

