3 OBJECTIVES AND ENDPOINTS

OBJECTIVES	ENDPOINTS
Primary	

 To evaluate in patients with IBS-D the abdominal pain response to BOS-589 after 4 weeks of treatment, relative to placebo (PBO). To evaluate the overall safety and tolerability of BOS-589 in the treatment of IBS-D during 4 weeks of treatment, relative to PBO. 	
 24-hour worst abdominal pain scores (WAP) at Day 29 compared to baseline (averaged over the week prior to each respective timepoint). Incidence of adverse events (AEs) serious adverse events (SAEs), discontinuations because of AEs, and any treatment-related severe AEs.
Secondary	

 To evaluate the treatment effect of BOS-589 on defecation after 4 weeks, relative to PBO. To evaluate the treatment effect of BOS-589 on IBS-related signs and symptoms. To evaluate the steady-state pharmacokinetics of BOS-589. 	
 Change in stool consistency, measured by the daily Bristol Stool Form Score (BSFS) at Day 29 compared to baseline (averaged over the week prior to each respective timepoint). Change in stool frequency, measured by the total number of spontaneous bowel movements in 24 hours at Day 29 compared to baseline (averaged over the week prior to each respective timepoint). Change in the IBS Severity Score (IBS-SS) at Day 29 compared to baseline. Change in the IBS Global Scale (IBS-GS) at Day 29 compared to baseline (averaged over the week prior to each respective timepoint). Maximum observed plasma concentration (C_{max}); time to C_{max} (T_{max}); minimum plasma concentration (C_{min}); area under the concentration versus time curve (AUC) from time zero to 4 hours postdose (AUC_{0-4}); AUC from time zero to the last quantifiable concentration (AUC_{0-t}).

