9.4.2 Safety Analyses

9.4.2.1 Adverse Events

Adverse events will be recorded from the time of consent until the Day 43/End-of-Study Follow-up visit. The number and percentage of patients with AEs will be displayed by system organ class and preferred term using Medical Dictionary for Regulatory Activities (MedDRA) Version 20.0 or higher, by study treatment. Summaries in terms of severity and relationship to investigational product will also be provided. All SAEs will be summarized in a similar manner. Patient listings of all AEs causing discontinuation of investigational product and all SAEs will be produced.

All AEs will be listed for individual patients showing both verbatim and preferred terms. Separate summaries of treatment-emergent SAEs and treatment-emergent AEs (TEAEs) related to investigational product will be generated.

Any event reported on the CRF that occurs on at the time of or after the initiation of investigational product is defined as treatment-emergent. Additionally, an AE that is reported to have started on Day 1 without an associated onset time will be assumed to have occurred after the initiation of investigational product. Hence, AEs occurring on Day 1 with no associated onset time will be assumed to be treatment emergent.

Serious AEs associated with a protocol-specified procedure and occurring after the time of consent but before administration of first dose of investigational product will be defined as non-treatment-emergent AEs (NTEAEs).

All safety analyses will be performed in the Safety Analysis Dataset.

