1. INTRODUCTION

The statistical analysis plan (SAP) details the planned analysis required to satisfy the Clinical Study Report of study number BOS-589-201: “A Phase 2a, Randomized, Double-blind, Placebo-controlled, Multicenter Study to Evaluate the Efficacy, Safety, and Tolerability of BOS-589 in the Treatment of Patients with Diarrhea-predominant Irritable Bowel Syndrome (IBS-D)”. The content of this SAP is based on the protocol amendment 2 (version 3.0) dated 12 Aug 2019.

Mock shells for tables, listings, and figures are in a separate document. Analyses for pharmacokinetics (PK) and pharmacodynamics (PD) will be governed by a separate SAP.

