2. STUDY OBJECTIVES AND ENDPOINTS

OBJECTIVES	ENDPOINTS
Primary	

 • To evaluate in patients with IBS-D the abdominal pain response to BOS-589 after 4 weeks of treatment, relative to Placebo. • To evaluate the overall safety and tolerability of BOS-589 in the treatment of IBS-D during 4 weeks of treatment, relative to Placebo. 	
 • 24-hour worst abdominal pain scores (WAP) at Day 29 compared to baseline (averaged over the week prior to each respective timepoint). • Incidence of adverse events (AEs) serious adverse events (SAEs), discontinuations because of AEs, and any treatment-related severe AEs.
Secondary	

 • To evaluate the treatment effect of BOS-589 on defecation after 4 weeks, relative to Placebo. • To evaluate the treatment effect of BOS-589 on IBS-related signs and symptoms. • To evaluate the steady-state PK of BOS-589. 	
 • Change in stool consistency, measured by the daily Bristol Stool Form Score (BSFS) at Day 29 compared to baseline (averaged over the week prior to each respective timepoint). • Change in stool frequency, measured by the total number of spontaneous bowel movements in 24 hours at Day 29 compared to baseline (averaged over the week prior to each respective timepoint). • Change in the IBS Severity Score (IBS-SS) at Day 29 compared to baseline. • Change in the IBS Global Scale (IBS-GS) at Day 29 compared to baseline (averaged over the week prior to each respective timepoint). • Maximum observed plasma concentration (C_{max}); time to C_{max} (T_{max}); minimum plasma concentration (C_{min}); area under the concentration versus time curve (AUC) from time zero to 4 hours postdose (AUC_{0-4}); AUC from time zero to the last quantifiable concentration (AUC_{0-t}).

Additional Objectives	Additional Endpoints
Exploratory (not included in protocol amendment 2 [version 3.0] dated 12 Aug 2019)	

 • To explore the treatment effect of BOS-589 in terms of weekly responders after 4 weeks of treatment, relative to Placebo. 	
 • Number of patients who are weekly responders, defined by both an abdominal pain intensity weekly responder (decrease in the weekly

Additional Objectives	Additional Endpoints

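### SAP v1.2 lists no cohort incidence for severe treatment-related AEs, a named primary safety component, and its rule for ungraded labs cannot count a low value

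*SAP*

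**What the plan says.** **AE tables.** Protocol 3 defines the primary safety endpoint as "Incidence of adverse events (AEs) serious adverse events (SAEs), discontinuations because of AEs, and any treatment-related severe AEs". SAP 2 repeats it, ending with "discontinuations because of AEs, and any treatment-related severe AEs". SAP 9.1 then lists its tables. The overview by cohort has rows for any TEAE, related TEAEs, moderate or severe TEAEs, "Any moderate or severe TEAEs related to study drug", serious events, discontinuations and deaths. The SOC/PT summaries include "All TEAEs by severity" and, separately, related TEAEs. Missing attributes are handled by worst case: "AEs with a missing severity will be classified as severe. AEs with a missing causality will be classified as related". For listings, "All AEs, including the verbatim and coded terms, will be listed for all enrolled patients". Protocol 9.4.2.1 states that "Summaries in terms of severity and relationship to investigational product will also be provided", without saying that the two are crossed. SAP 1 notes that "Mock shells for tables, listings, and figures are in a separate document"; those shells were not available.

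**Ungraded laboratory measures.** SAP 9.2 counts values from 2.5 to below 5.0 times, and at 5.0 times or more, the upper or the lower limit of normal. It plans separate low-side counts only for parameters that are toxicity-graded in both directions.

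**Treatment emergence.** SAP 9.1 and Protocol 9.4.2.1 treat any event from first dose onward as a TEAE. Appendix 1 of the SAP names a fully dated event a TEAE only if it starts before end of treatment plus 15 days. It is silent on later events and sets no such limit for partial or missing start dates.

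**The concern.** The endpoint is an incidence, to be judged relative to placebo. Three of its four components have a row in 9.1; the fourth does not. SAP 3.2, which records changes from the protocol, does not say that this component was dropped. Protocol 6.5 also uses a treatment-related severe AE as its trigger for interrupting study treatment, so a reader of the study report will look for this count.

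The laboratory rule fails on one side. As written, the categorical summary would show no low abnormality for any ungraded measure, whatever the data, and could report normal values as abnormal. The treatment-emergence mismatch is minor: a programmer must decide whether the appendix limits the definition in 9.1.

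**Working it through.** **1. Can the severe related incidence be recovered from the listed tables?**

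Inputs: 44 patients per cohort (SAP 3.4) and the table list in SAP 9.1. The AE data are assumed: 12 patients with one non-serious TEAE each, in four PTs of 3 patients.

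| | PTs 1 and 2 | PTs 3 and 4 |
|---|---|---|
| Dataset A | severe unrelated; moderate related; moderate related | severe unrelated; moderate related; mild related |
| Dataset B | severe related; moderate related; moderate unrelated | severe related; mild related; moderate unrelated |

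Overview counts:

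| Row | A | B |
|---|---|---|
| Any TEAE | 12 | 12 |
| Related | 2×2 + 2×2 = 8 | 2×2 + 2×2 = 8 |
| Moderate or severe | 2×3 + 2×2 = 10 | 2×3 + 2×2 = 10 |
| Moderate or severe, related | 2×2 + 2×1 = 6 | 2×2 + 2×1 = 6 |
| **Severe and related (not planned)** | **0** | **4** |

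The PT tables also agree. PTs 1 and 2 each have 1 severe, 2 moderate and 2 related. PTs 3 and 4 each have 1 severe, 1 moderate, 1 mild and 2 related. The Clopper-Pearson 95% intervals are 0 to 8.0% for 0/44 and 2.5 to 21.7% for 4/44 (9.1%).

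In general, for a PT with n patients, s severe and r related, and one event per patient, the severe related count lies between max(0, s + r − n) and min(s, r).

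- Here n = 3, s = 1, r = 2 gives 0 to 1 per PT, so 0 to 4 over four PTs. A and B are the two ends.
- With n = 8, s = 4, r = 6 the bounds are 2 to 4, so other data narrow the range.
- The bounds coincide only when s is 0 or n, or r is 0 or n (checked for all n up to 44).

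**2. Ungraded laboratory rule**

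If LLN > 0 and value < LLN, then value/LLN < 1 < 2.5. Since ULN exceeds LLN, the value cannot reach 2.5 × ULN either. Low values counted: 0. A grid of 60,000 combinations of value, LLN and ULN, with values from 0 to 0.999 × LLN, also gave 0.

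Read literally, the LLN multiples can reach into the normal range. With q = ULN/LLN (assumed, as the documents give no reference ranges), the share of the range's width at or above 2.5 × LLN is max(0, (q − 2.5)/(q − 1)):

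| q | 2 | 2.5 | 3 | 4 | 6 |
|---|---|---|---|---|---|
| Share | 0% | 0% | 25% | 50% | 70% |

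At q = 6, (6 − 5)/(6 − 1) = 20% of the width falls in the upper class. These are shares of width, not of patients.

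**3. Treatment emergence**

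The first onset day on which Appendix 1 is silent is end of treatment + 15. Silent days up to the End-of-Study visit = max(0, visit day − first silent day + 1). The visit window is Day 43 ± 3.

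| End of treatment | First silent day | Visit Day 40 | Day 43 | Day 46 |
|---|---|---|---|---|
| Day 28 (last dose, SAP 5.2) | 43 | 0 | 1 | 4 |
| Day 29 (visit, usage in SAP 9) | 44 | 0 | 0 | 3 |
| Day 14 (early stop, followed to End of Study) | 29 | 12 | 15 | 18 |

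The last row applies only if such patients attend that visit, on which Protocol 7.1 and 8.1 differ.

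**The case against.** The best reply on the AE table is that nothing is lost. Severity and relationship are both collected, missing values have rules, all AEs are listed, and SAP 4 sorts listings by cohort, so the numerator can be counted by hand. The mock shells may hold the row. The pooled moderate-or-severe related row is an upper bound, many PTs may have no severe case and so no ambiguity, and the example was built to show the ambiguity. No test or decision rule depends on the row.

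All of that is fair, and it limits the point to an omitted summary. It does not remove it. A listing is not a planned incidence, and a named primary component belongs in the SAP, which takes precedence over the protocol on analysis details (Protocol 9.4).

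On the laboratory rule, a fraction of the lower limit was probably meant. The documents do not say which tests are ungraded or what their reference ranges are, so the practical reach is unknown. Low values still enter the descriptive summaries, the most-extreme-change summary and the listings, and parameters graded in both directions have a working low-side count. These limits stand, but the written threshold still cannot do its job on the low side.

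On treatment emergence, silence in the appendix is not a contrary classification, and 9.1 read alone still makes late events TEAEs. That is why it is rated minor.

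**Conclusion.** Both main points hold on the text of SAP v1.2.

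- **AE component.** No listed table gives the cohort incidence of severe related TEAEs, and the listed tables do not in general determine it. The 0/44 versus 4/44 contrast shows that the ambiguity can occur. It does not predict its size in this trial, and it rests on the assumed event pattern with one event per patient.
- **Ungraded labs.** The count of low values is zero by construction for any measure with a positive lower limit. Flagging of normal values needs a ULN/LLN ratio of at least 2.5 and a literal reading. The defect is confined to the categorical count for ungraded measures.
- **Treatment emergence.** This is an inconsistency between the body and the appendix. For completers it affects at most 4 onset days.

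None of this threatens the data or the efficacy analysis. It should be corrected because it concerns how part of a primary endpoint is reported.

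**What to change.** 1. Add a row to the SAP 9.1 overview table for patients with any severe TEAE related to study drug, and a matching SOC/PT summary.
2. In SAP 9.2, apply the 2.5 and 5 multiples to the ULN only. Define the low side from the minimum post-baseline value as sponsor-set fractions of the LLN, for example LLN/2.5 = 0.40 × LLN and LLN/5 = 0.20 × LLN.
3. Delete the 15-day limit from the AE table in Appendix 1, or state one limit in 9.1 and apply it to every date type.

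The cost is SAP wording, one overview row and one SOC/PT summary. No new data are needed.
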